### **7.5.1 PRINCIPAL INVESTIGATOR/RESEARCH TEAM**

The clinical research team will meet on a regular basis when patients are being actively treated on the trial to discuss each patient. Decisions about dose modification or discontinuation will be determined.

All data will be collected in a timely manner and reviewed by the principal investigator or a designated associate investigator. Adverse events will be reported as required above. Any safety concerns, new information that might affect either the ethical and or scientific conduct of the trial, or protocol deviations and violations will be immediately reported to the IRB using iRIS and if applicable to the FDA and drug manufacturer.

The principal investigator will review adverse event and response data on each patient to ensure safety and data accuracy. The principal investigator will personally conduct or supervise the investigation and provide appropriate delegation of responsibilities to other members of the research staff.

### **7.5.2 SPONSOR MONITORING PLAN**

As a sponsor for clinical trials, FDA regulations require the CCR to maintain a monitoring program. The CCR's program allows for confirmation of: study data, specifically data that could affect the interpretation of primary study endpoints; adherence to the protocol, regulations, and SOPs; and human subjects protection. This is done through independent verification of study data with source documentation focusing on:

- Informed consent process
- Eligibility confirmation
- Drug administration and accountability
- Adverse events monitoring

- Response assessment.

The monitoring program also extends to multi-site research when the CCR is the coordinating center.

This trial will be monitored by personnel employed by a CCR contractor. Monitors are qualified by training and experience to monitor the progress of clinical trials. Personnel monitoring this study will not be affiliated in any way with the trial conduct.

## **8 STATISTICAL SECTION**

### **8.1 PRIMARY ENDPOINT**

The study will be conducted as a small, optimal two-stage phase II trial(49), in order to rule out an unacceptably low 5% overall response rate (ORR;  $p_0=0.05$ ), in favor of a slightly higher response rate of 25% ( $p_1=0.25$ ). With  $\alpha=0.10$  (probability of accepting a poor treatment=0.10) and  $\beta = 0.10$  (probability of rejecting a good treatment=0.10), the study will initially enroll 9 evaluable patients and if 0 of the 9 have a response, then no further patients will be accrued. If 1 or more the first 9 (11.1% or more) have a response, then accrual would continue until a total of 24 patients have enrolled. Only complete responses (CR) and partial responses (PR) will be counted towards the overall response rate. As it may take several weeks to months to determine if a patient has experienced a response, a temporary pause in the accrual to the trial may be necessary to ensure that enrollment to the second stage is warranted. If there are 1 to 2 responses in 24 patients, this would be an uninterestingly low response rate, while if there were 3 or more responses in 24 (12.5% or more) patients, then this would be sufficiently interesting to warrant further study in later trials. Under the null hypothesis (5% response rate), the probability of early termination is 63%.

### **8.2 ANALYSIS OF SECONDARY ENDPOINTS**

#### *Safety and Tolerability*

Patients will be carefully monitored for adverse events; which will be recorded in a daily patient diary and documented by the care providers. These will be graded according to CTCAE version 4.0. Information regarding type of adverse event, grade, attribution, temporal occurrence and frequency will be summarized using descriptive methods.

#### *Progression-Free Survival (PFS) and Overall Survival*

The progression free survival and overall survival for all patients enrolled on the trial will also be determined using Kaplan-Meier curves and reported along with their associated 95% two-sided confidence intervals at selected time points.

#### *Analysis of Exploratory Pharmacodynamic Endpoints*

A variety of biologic parameters will also be evaluated and the results reported as exploratory and hypothesis generating, without adjustment for multiple comparisons.

*Analysis of patients' health-related quality of life (as measured by patient and parent report PROMIS measures) and patient-reported symptoms (as measured by the Distress and Symptom Checklist)*

Patient's PROMIS scores (patient and parent report for minors) will be converted to t-scores and recorded at each time point. Assuming accrual of 24 patients, T-scores at baseline, first staging and study endpoint will be compared using repeated measures ANOVA to detect significant changes over time. While the sample size will not permit controlling for gender, age group, or disease status, scores will be descriptively reported stratified by these variables. Additionally, PROMIS scores that fall more than 1 standard deviation below the mean will be considered to reflect low QOL. Patient reported symptoms on the Distress and Symptom Checklist will be evaluated using frequency distributions and will be descriptively followed over the course of treatment on this protocol. These data will be reported as exploratory and hypothesis generating, without adjustment for multiple comparisons.

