#### Pediatric Physical Function - Mobility - Short Form

Please respond to each item by marking one box per row.

In the past 7 days....

	With no trouble	With a little trouble	With some trouble	With a lot of trouble	Not able to do
I could do sports and exercise that other kids my age could do.	 4	 3	 2	 1	 0
I could get up from the floor.	 4	 3	 2	 1	 0
I could keep up when I played with other kids.	 4	 3	 2	 1	 0
I could move my legs.	 4	 3	 2	 1	 0
I could stand up by myself.	 4	 3	 2	 1	 0
I could stand up on my tiptoes.	 4	 3	 2	 1	 0
I could walk up stairs without holding on to anything.	 4	 3	 2	 1	 0
I have been physically able to do the activities I enjoy most.	 4	 3	 2	 1	 0

PROMIS™ Pediatric Item Bank v.1.0 - Anxiety - Short Form 8a

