### Pediatric Anxiety - Short Form

Please respond to each item by marking one box per row.

**In the past 7 days....**

	Never	Almost Never	Sometimes	Often	Almost Always
I felt nervous.	 0	 1	 2	 3	 4
I felt scared.	 0	 1	 2	 3	 4
I felt worried.	 0	 1	 2	 3	 4
I felt like something awful might happen.	 0	 1	 2	 3	 4
I thought about scary things.	 0	 1	 2	 3	 4
I was afraid that I would make mistakes.	 0	 1	 2	 3	 4
I worried about what could happen to me.	 0	 1	 2	 3	 4
I worried when I went to bed at night.	 0	 1	 2	 3	 4

PROMIS™ Pediatric Item Bank v.1.0 - Depressive Symptoms - Short Form 8a

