### Pediatric Depressive Symptoms - Short Form

Please respond to each item by marking one box per row.

**In the past 7 days....**

	Never	Almost Never	Sometimes	Often	Almost Always
I could not stop feeling sad.	 0	 1	 2	 3	 4
I felt alone.	 0	 1	 2	 3	 4
I felt everything in my life went wrong.	 0	 1	 2	 3	 4
I felt like I couldn't do anything right.	 0	 1	 2	 3	 4
I felt lonely.	 0	 1	 2	 3	 4
I felt sad.	 0	 1	 2	 3	 4
I felt unhappy.	 0	 1	 2	 3	 4
I thought that my life was bad.	 0	 1	 2	 3	 4

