**Pediatric Fatigue - Short Form**

Please respond to each item by marking one box per row.

**In the past 7 days.....**

	Never	Almost Never	Sometimes	Often	Almost Always
Being tired made it hard for me to play or go out with my friends as much as I'd like.	 0	 1	 2	 3	 4
I felt weak.	 0	 1	 2	 3	 4
I got tired easily.	 0	 1	 2	 3	 4
Being tired made it hard for me to keep up with my schoolwork.	 0	 1	 2	 3	 4
I had trouble finishing things because I was too tired.	 0	 1	 2	 3	 4
I had trouble starting things because I was too tired.	 0	 1	 2	 3	 4
I was so tired it was hard for me to pay attention.	 0	 1	 2	 3	 4
I was too tired to do sports or exercise.	 0	 1	 2	 3	 4
I was too tired to do things outside.	 0	 1	 2	 3	 4
I was too tired to enjoy the things I like to do.	 0	 1	 2	 3	 4

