### Pediatric Pain Interference - Short Form

Please respond to each item by marking one box per row.

In the past 7 days.....

	Never	Almost Never	Sometimes	Often	Almost Always
I had trouble sleeping when I had pain.	 0	 1	 2	 3	 4
I felt angry when I had pain.	 0	 1	 2	 3	 4
I had trouble doing schoolwork when I had pain.	 0	 1	 2	 3	 4
It was hard for me to pay attention when I had pain.	 0	 1	 2	 3	 4
It was hard for me to run when I had pain.	 0	 1	 2	 3	 4
It was hard for me to walk one block when I had pain.	 0	 1	 2	 3	 4
It was hard to have fun when I had pain.	 0	 1	 2	 3	 4
It was hard to stay standing when I had pain.	 0	 1	 2	 3	 4

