### Pediatric Peer Relationships - Short Form

Please respond to each item by marking one box per row.

**In the past 7 days....**

	Never	Almost Never	Sometimes	Often	Almost Always
I felt accepted by other kids my age.	 0	 1	 2	 3	 4
I was able to count on my friends.	 0	 1	 2	 3	 4
I was able to talk about everything with my friends.	 0	 1	 2	 3	 4
I was good at making friends.	 0	 1	 2	 3	 4
My friends and I helped each other out.	 0	 1	 2	 3	 4
Other kids wanted to be my friend.	 0	 1	 2	 3	 4
Other kids wanted to be with me.	 0	 1	 2	 3	 4
Other kids wanted to talk to me.	 0	 1	 2	 3	 4

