**Fatigue - Short Form 7a**

**Please respond to each question by marking one box per row.**

**In the past 7 days...**

		Never	Rarely	Sometimes	Often	Always
FATEXP20	How often did you feel tired?.....	 1	 2	 3	 4	 5
FATEXP5	How often did you experience extreme exhaustion?.....	 1	 2	 3	 4	 5
FATEXP18	How often did you run out of energy?.....	 1	 2	 3	 4	 5
FATIMP33	How often did your fatigue limit you at work (include work at home)?.....	 1	 2	 3	 4	 5
FATIMP30	How often were you too tired to think clearly?.....	 1	 2	 3	 4	 5
FATIMP21	How often were you too tired to take a bath or shower?.....	 1	 2	 3	 4	 5
FATIMP40	How often did you have enough energy to exercise strenuously?.....	 5	 4	 3	 2	 1

PROMIS Item Bank v1.0 – Pain Interference - Short Form 6b

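### The low-QOL cut-off in Section 8.2 points the wrong way on the anxiety, depressive symptoms, fatigue and pain interference forms, provided T-scores keep the printed direction

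*Combined protocol and SAP*

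**What the plan says.** The QOL paragraph of Section 8.2 converts PROMIS scores (patient report, plus parent report for minors) to T-scores. It compares baseline, first staging and study endpoint by repeated measures ANOVA, and reports scores descriptively by gender, age group and disease status. It then adds a classification: "PROMIS scores that fall more than 1 standard deviation below the mean will be considered to reflect low QOL". The sentence covers all PROMIS scores. It makes no exception by form, and no reversal step appears there or elsewhere in the protocol. The same paragraph calls the QOL data exploratory and hypothesis generating.

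The forms are printed in Appendix 12 (pediatric), Appendix 13 (parent proxy) and Appendix 14 (adult), six per set, with the code for each answer. Two kinds of form appear:

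- **Function and social forms.** The pediatric mobility item "I have been physically able to do the activities I enjoy most" gives 4 for no trouble and 0 for not able. The peer relationships item "I felt accepted by other kids my age" gives 0 for never and 4 for almost always. A high score is good.
- **Symptom forms.** The items "I felt like something awful might happen" (anxiety), "I could not stop feeling sad" (depressive symptoms), "I had trouble starting things because I was too tired" (fatigue) and "It was hard for me to pay attention when I had pain" (pain interference) also run from 0 for never to 4 for almost always. A high score is bad.

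Section 8.3 records that nine patients and their parents were enrolled before accrual closed.

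**The concern.** A cut below the mean identifies poor QOL only where a low score is a poor score. On the symptom forms a low score means few symptoms, so the rule read literally puts the low-QOL label on the least affected patients and leaves the most affected unlabelled. The reported proportion would also move the wrong way: as the cohort's anxiety, depression, fatigue or pain worsened, the share called low QOL would fall.

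The affected domains matter to this study. Section 1.2.3 reports frequent chronic pain and significant anxiety in the clinic's own earlier screening of GIST patients, and it gives anxiety and depression as known vandetanib toxicities that these instruments are meant to examine. A reader of the final report would take the low-QOL figures on those forms at face value.

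**Working it through.** The plan gives no figure for this rule, so there is none to reproduce. The check is of direction first and size second.

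**1. Direction of each form.** Inputs are the printed answer codes and item counts in Appendices 12 to 14. The table gives the raw total in the best health state, then in the worst.

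| Domain | Pediatric | Parent proxy | Adult | Higher means |
|---|---|---|---|---|
| Mobility / physical function | 32, 0 | 32, 0 | 50, 10 | better |
| Peer relationships | 32, 0 | 28, 0 | not used | better |
| Anxiety | 0, 32 | 0, 32 | 7, 35 | worse |
| Depressive symptoms | 0, 32 | 0, 24 | 8, 40 | worse |
| Fatigue | 0, 40 | 0, 40 | 7, 35 | worse |
| Pain interference | 0, 32 | 0, 32 | 6, 30 | worse |

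The sixth adult form, Global Health, has seven items printed higher = better and three (Global07, Global08, Global10) printed higher = worse.

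Forms keyed higher = worse: 4 domains × 3 sets = 12 of 18.

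**2. Is the keying deliberate?** The adult fatigue form has one positively worded item, FATIMP40: "How often did you have enough energy to exercise strenuously". It is printed with Never = 5 down to Always = 1, while the other six items run from Never = 1 to Always = 5. The form is therefore built so that a higher total means more fatigue.

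**3. Overlap of the two rules.** On a higher = worse form the stated rule flags scores below mean − 1 SD. A rule matched to direction flags scores above mean + 1 SD. No score can satisfy both, so the overlap is 0, whichever mean and SD are used.

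**4. Illustrative rates with a fixed reference mean.** Assumptions, none of them from the documents: normal scores, cohort SD equal to the reference SD, and cohort mean d SD worse than the reference. Then

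- stated rule: Φ(−1 − d)
- direction-matched rule: 1 − Φ(1 − d)

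| d | Stated rule | Matched rule | Of 9 patients, stated v matched |
|---|---|---|---|
| 0 | 15.9% | 15.9% | 1.4 v 1.4 |
| 0.25 | 10.6% | 22.7% | 1.0 v 2.0 |
| 0.5 | 6.7% | 30.9% | 0.6 v 2.8 |
| 1 | 2.3% | 50.0% | 0.2 v 4.5 |

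Even at d = 0, where the counts agree, the patients flagged are opposite ones.

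**5. Illustrative rates with the study's own mean and SD.** For normal data, the chance that a given score lies more than 1 sample SD below the sample mean is the tail of a t distribution on n − 2 df beyond √(n(n − 2)) / √((n − 1)² − n). For n = 9 this is √63 / √55 = 1.070 on 7 df, a tail of 0.160 on each side. That is 9 × 0.160 = 1.4 patients under either rule, whatever the shift, but again opposite patients. For n = 7 and n = 5 the tail is 0.161 and 0.164. A simulation of 400,000 samples of nine gave 0.1599 on each side.

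Nine is an upper bound for any one form. Adults and minors complete different forms, self-report starts at age 8, and completion requires consent and English or Spanish (Sections 2.5.3, 3.1.1 and 3.4).

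**The case against.** The strongest counter-argument is that the cut applies to T-scores and the documents contain no conversion table. The printed codes settle only the raw direction, and FATIMP40 shows how the instrument keys its items, not how this team will orient the converted scores. An analyst might also read the sentence for its purpose and put the cut on the poorer side of each form. In addition, the label feeds no test, stopping rule or decision, the T-scores are reported in any case, and anxiety, depression and sleep are also recorded on the Distress and Symptom Checklist.

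The dependence on conversion stands as a condition on the conclusion. It does not clear the plan: nothing states that the conversion flips direction, and if it did the plan would have to say so. The charitable reading requires the analyst to depart from a sentence that says below the mean. The point about consequence stands in full and sets the severity. It is also fair to say that the shifts of 0.25 to 1 SD are assumptions. The zero overlap needs none of them.

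**Conclusion.** The concern holds, at minor severity. Provided T-scores keep the printed direction, the stated rule is wrong on 12 of the 18 forms: it selects patients at the low-symptom end and cannot select anyone with above-average symptoms. It is right for mobility or physical function and for peer relationships. The zero overlap follows from direction alone. The percentages rest on the assumed normality and shifts.

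The primary response endpoint is untouched, and the ANOVA of T-scores does not use the cut-off.

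Two further omissions are lesser matters of detail. The sentence does not say whether its mean and SD are those of the PROMIS reference population or of the study sample. No scoring is named for adult Global Health, whose three opposite items would distort that form's own T-score and ANOVA if they were not aligned.

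**What to change.** Replace the sentence in Section 8.2 with wording such as:

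> Low QOL is a T-score more than 1 SD worse than the mean: above mean + 1 SD for anxiety, depressive symptoms, fatigue and pain interference, and below mean − 1 SD for mobility or physical function and peer relationships. The same directions apply to the parent-proxy forms.

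Add one sentence naming the mean and SD used, and one stating that adult Global Health is scored by its instrument's own rules, with Global07, Global08 and Global10 aligned to the other items as those rules require (Global07 is printed 0 to 10, so reversal alone may not be enough) and low QOL on the worse side. Confirm the direction of the T-score conversion when making the change.

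The cost is three or four sentences. No new data are needed and no test changes. The team must take the Global Health scoring rules, and the reference mean and SD if those are chosen, from the instrument documentation.

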### **8.3 ACCRUAL TARGET AND STUDY DURATION**

A total of 24 evaluable patients may need to be enrolled to meet the primary objective of this study, if 1 or more of the first 9 patients has a response. The actual accrual ceiling will be set at 27 to allow for the possibility of a small number of inevaluable patients (withdrawal prior to meeting progression or toxicity) being enrolled. It is anticipated that 1-2 patients per month may enroll on this trial for the first 6 months, and then approximately 6-8 patients per year thereafter. Thus, 2 to 3 years is anticipated as the accrual period for this study.

Please Note: Nine patients and their parents were enrolled on the study before it was closed to accrual. The parents were not included in the initial accrual ceiling of 27; but they need to be accounted for. Because the study is no longer recruiting, it is not necessary to increase the accrual ceiling; the parents will be included in the 27.

## **9 COLLABORATIVE AGREEMENTS**

### **9.1 AGREEMENT TYPE**

AstraZeneca has agreed to provide the drug (vandetanib) to patients participating in this clinical trial. The trial will be performed under a Clinical Trial Agreement (NCI CTA #00940-13) with AstraZeneca.

## **10 HUMAN SUBJECTS PROTECTIONS**

### **10.1 RATIONALE FOR SUBJECT SELECTION**

Patients of both genders, from all racial and ethnic groups are eligible for this trial if they meet the eligibility criteria outlined in [Section 2.1](#). There is no clinical information that suggests differences in vandetanib metabolism or response among racial or ethnic groups or between the genders, indicating that results of the trial will be applicable to all groups. This phase II trial of vandetanib will be conducted in children greater than two years of age and adults measurable wt-GIST which is considered a low prevalence disease. Efforts will be made to extend the accrual to a representative group from this population, but with a rare disease and with a planned accrual of 24 patients, a balance must be struck between completing the trial in a timely fashion on the one hand and the need to explore gender, racial, and ethnic aspects of clinical research on the other. If differences in outcome that correlate to gender, racial, or ethnic identity are noted, accrual may be expanded or additional studies may be performed to investigate those differences more fully.

## **10.2 PARTICIPATION OF CHILDREN**

This trial is designed to determine the response rate of wt-GIST to vandetanib in children and adults. There is currently no experience with vandetanib in wt-GIST, so the tolerability of vandetanib and the toxicity are also being studied. The safety of vandetanib dosing in children has been established in NCI protocol 07-C-0189. Children and adolescents will be enrolled onto this research trial, which will be conducted by pediatric oncologists who have extensive experience in performing investigational drug trials in children. Patients enrolled at the POB, NCI will be cared for in the POB outpatient clinic or day hospital. When patients require hospital admission, they will be cared for on the 1NW Pediatric Unit by the POB staff or on the adult inpatient unit by the MOB staff.

## **10.3 PARTICIPATION OF SUBJECTS UNABLE TO GIVE CONSENT**

Adults unable to give consent are excluded from enrolling in the protocol. However, re-consent may be necessary and there is a possibility, though unlikely, that subjects could become decisionally impaired. For this reason and because there is a prospect of direct benefit from research participation (section 10.5), all subjects  $\geq$  age 18 will be offered the opportunity to fill in their wishes for research and care, and assign a substitute decision maker on the “NIH Advance Directive for Health Care and Medical Research Participation” form so that another person can make decisions about their medical care in the event that they become incapacitated or cognitively impaired during the course of the study. Note: The PI or AI will contact the NIH Ability to Consent Assessment Team for evaluation. For those subjects that become incapacitated and do not have pre-determined substitute decision maker, the procedures described in MAS Policy 87-4 for appointing a surrogate decision maker for adult subjects who are (a) decisionally impaired, and (b) who do not have a legal guardian or durable power of attorney, will be followed.

## **10.4 EVALUATION OF BENEFITS AND RISKS/DISCOMFORTS**

### **10.4.1 RISKS OF VANDETANIB**

The primary risk to patients participating in this research study is from toxicity of vandetanib. In adults, vandetanib has been relatively well tolerated. The most common adverse events have been rash, diarrhea and asymptomatic QTc prolongation, which are reversible and generally can be alleviated by dose reduction. In the ongoing NCI protocol 07-C-0189 the most common toxicities in children have been diarrhea, rash, and TSH elevation. The response rate in subjects with wt-GIST is unknown, but vandetanib has shown clinical activity in MTC. A complete summary of Vandetanib risks is contained in Section 11.1.6.

### **10.4.2 RISK OF FDG-PET (OPTIONAL)**

The additional risks of one optional FDG-PET are expected to be minimal and are related to the risks of the F-18 FDG tracer agent injection, which include rare cases of transient hypotension, hyper- or hypoglycemia and transient increases in alkaline phosphatase. Pregnant or breast-feeding women will not be allowed to participate in this study and should not be exposed to FDG contrast agent injection as the effects on a fetus or growing child are not known. This optional scan will be limited to consenting participants who do not require sedation to lie still for the duration of the scan.

